10.7 Blinding and procedures for breaking the blind

This is a double-blind study; only the pharmacists dispensing the IP and the unblinded CRA will know the treatment allocation of the participants. The site staff, parents/guardians of participants, sponsor, and monitoring personnel will be blind to treatment arm allocations.

To maintain the blind, the identity of the IP in each dispensed syringe will not be indicated on the label.

The laboratory personnel completing assays on routine stool samples will have potential deductive knowledge of the participants' treatment allocation as a result of conducting assays. For this reason, communication will be restricted between the laboratory personnel and blinded study personnel, until after final database lock.

Only in a medical emergency, when the investigator determines that adequate medical care cannot be provided without knowing the treatment assignment, the blind may be broken. In this instance the Investigator may contact the Pharmacy to obtain the treatment identity. If possible, such emergencies should be discussed with the Medical Monitor before breaking the blind. Details for contacting the Medical Monitor will be provided in the SRM.

If the blind has been broken, the investigator must document the date and the reason the blind was broken in the participant's notes and CRF.

The study monitor should be notified if the blind is broken. MCRI or designee will decide on a case-by-case basis whether unblinded infants will receive further doses of IP.

10.8 Preparation and Dispensing of IP

The pharmacist will prepare and dispense the appropriate dose of IP, according to the participant's allocated treatment schedule.

Dose preparation and transport to sites is described in the Pharmacy Manual and SRM.

10.9 IP administration and treatment compliance

Prior to administration of the second, third and fourth doses of IP, participants will be given a 2ml oral dose of an antacid solution (Mylanta® Original), using a syringe without a needle. The antacid solution is administered to help neutralise stomach acid to ensure vaccine stability when administered to infants. The neonatal stomach is less acidic, so the antacid solution is not required for the first dose of IP.

The investigator or designee will administer the IP to the participant within 10 minutes after administering the antacid (where applicable). The participant should be held in a supine position, and the entire contents of the syringe administered orally to the inside of the cheek in small aliquots, taking care that the participant does not spit the IP out.

The participant must remain under supervision at the clinic for at least 30 minutes after administration of the IP.

A participant will be considered compliant with study treatment if they received the scheduled administration of all doses of the IP, within the protocol specified time windows.

10.9.1 Incomplete administration of IP

Participants who do not ingest the full 1 mL dose of IP (e.g. due to spitting out the IP or vomiting within the 30 minutes following administration) will not receive any further IP at that visit. The participant will however, continue to receive subsequent doses of the IP as per protocol.

Any incomplete administration of IP will be recorded in the participant notes and the CRF.

10.9.2 Criteria for temporary delay of IP dose

Administration of any dose of IP can be delayed at the discretion of the investigator or Medical Monitor.

For the second, third and fourth doses, if a participant has a fever (paediatrics: $\geq 37.5^{\circ}$ C axillary/oral or $\geq 38.0^{\circ}$ C rectal/tympanic) and/or acute illness that contraindicates vaccination, dosing will be delayed until the participant is afebrile. If the dose then falls outside of the protocol specified window it will be recorded as a protocol deviation.

11 ADVERSE EVENTS

The definitions of AEs and SAEs are given below. It is extremely important that all staff involved in the trial are familiar with the content of this section. The PI is responsible for ensuring this.

11.1 Adverse event definitions

An AE is any untoward medical occurrence in a participant administered a pharmaceutical product and which does not necessarily have a causal relationship with this treatment. An AE can therefore be any unfavourable and unexpected sign, symptom, or disease temporally associated with the use of an IP, whether or not related to the IP.

Pre-existing diseases are not considered AEs unless there is a change in frequency or severity. This change has to be reflected in the reported term. Lack of efficacy is not considered an AE, per se.

Parents/guardians must be instructed to inform the Investigator about all participant AEs and these must be documented in the participant records and Case Report Form (CRF) together with their intensity;

- Mild (Grade 1) AEs do not impact normal daily routine.
- Moderate (Grade 2) AEs impact the normal daily routine
- Severe (Grade 3) are those AEs which make normal daily routine impossible.
- Life Threatening (Grade 4)
- Fatal (Grade 5)

An AE that is assessed as severe should not be confused with a SAE. Severity is a category utilised for rating the intensity of an event, and both AEs and SAEs can be assessed as severe. An event is defined as 'serious' when it meets one of the pre-defined outcomes as described in Section 11.2.

The Investigator must assign causality to each adverse event in relation to RV3-BB based on the following scale:

- Not related: AE for which there is evidence of another explanation, e.g. the adverse event is obviously explained by a concurrent disease(s), is in accordance with the known effect of a concomitant medication, or has occurred prior to first administration of IP.
- Unlikely related: AE with a time to IP administration that makes a relationship improbable (but not impossible), and disease or other drugs provide plausible explanations.
- Possibly related: AE with a reasonable time relationship to IP administration, but which could also be explained by disease or other drugs.
- Probably related: AE with reasonable time relationship to IP administration that is unlikely to be attributed to disease or other drugs.
- Definitely related: AE with plausible time relationship to IP administration which cannot be explained by disease or other drugs, and event is definitive pharmacologically

or phenomenologically (i.e. an objective and specific medical disorder or a recognised pharmacological phenomenon).

All AEs must be documented by the Investigator, regardless of causality.

Expected AEs are defined as all AEs stated as such in the IB. If an AE has not been previously reported as expected (including type, degree, or frequency) in the IB, it is an unexpected adverse event. MCRI or designee is responsible for determining the expectedness of an AE.

If an AE leads to premature discontinuation of the study, the appropriate pages of the CRF must be completed.

11.2 Serious Adverse Events

An AE shall be defined as serious if it:

- results in death;
- is life-threatening;
 - Life threatening in the definition of serious refers to an event in which the participant was at risk of death at the time of the event, it does not refer to an event which hypothetically might have caused death if it were more severe.
- requires inpatient hospitalisation or prolongation of an existing hospitalisation;
 - Hospitalisation is defined as in-patient admission or care regardless of duration.
 - Out-patient treatment in an emergency room is not in itself an SAE, although the reasons for it may be (e.g. bronchospasm, laryngeal oedema). Elective surgery, hospitalisation for social reasons (with no causal AE), or hospital admissions and/or surgical operations planned before or during this study are not considered AEs if the illness or disease existed before the participant was enrolled in the study, provided that it did not deteriorate in an unexpected way during the study.
- results in a persistent or significant disability or incapacity;
- is an important medical event
 - This includes events that may not be immediately life-threatening or result in death or hospitalisation but may jeopardise the participant or may require intervention to prevent one of the other outcomes listed above.

11.2.1 SAE exceptions

Conditions identified as a congenital anomaly or birth defect, regardless of when the condition is identified, will not be recorded as SAEs unless the condition progresses/worsens or is fatal. These conditions should be recorded as medical history, even if they are identified/diagnosed after randomisation.

11.3 Recording of AEs

AEs will be captured from the time of first dose of IP until the final study visit. Parents/guardians will be asked at each visit whether their baby has experienced any AEs.

SAEs that are at least possibly or definitely related to IP occurring to a study participant after the AE reporting period will be reported to the sponsor if the Investigator becomes aware of them.

It is preferable that AEs are reported as diagnoses if one is able to be made, rather than individual signs and symptoms. The AE description, start and stop dates, severity, causality and outcome must be recorded, as well as any actions taken.

Unless a diagnosis is made, or signs and symptoms are present, an abnormal laboratory value or vital sign should only be reported as AEs if they cause the participant to discontinue from the trial, the investigator feels they are clinically significant, or they meet a criterion for a SAE.

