	 Serum anti-rotavirus IgA response (defined as a ≥3 fold increase from baseline) at each serum collection time-point to 4 weeks after 3 doses of RV3-BB. Vaccine take defined as at least a threefold increase in serum anti-rotavirus immunoglobulin A (IgA) from baseline to post IP dosing, or detectable RV3 shedding in stools (by ELISA or PCR) any day from day 3 to 5 following administration of IP. Cumulative vaccine take defined as vaccine take observed at the current assessment time point or following any previous dose. Anti-rotavirus IgA response (defined as at least a threefold increase from baseline to post IP dosing) at each serum collection time point. Presence of RV3 shedding in stools (by ELISA or PCR) from day 3 to 7 following each dose of IP.

	 Anti-rotavirus IgA titres defined as geometric mean titres at each serum collection time point. Episodes of diarrhea, from the time of randomisation to 28 days following the last dose of IP. Episodes will be confirmed by Rotavirus antigen ELISA on samples. Safety and tolerability Safety and tolerability will be assessed through: Unsolicited Adverse Events (AE) in the days 0-28 following each dose of IP. Serious Adverse Events (SAE) from the first dose of IP until 28 days post last dose of IP.
	• Review of episodes of blood in stool.
	Exploratory
	Exploratory endpoints will be assessed through:
	 HBGA Lewis and secretor status will be determined by ELISA/PCR on saliva collected at Visits 1, 3, 5 and 7 and using whole blood at week 18 for non secretors. Maternal serum IgA and IgG response will be determined on maternal serum sample collected pre study or at Visit 1. Bacterial taxonomic and genetic functional profiling of stool microbiome will be conducted on maternal stool samples and participant stool samples collected post administration of IP and at birth (prior to first IP dose). B and T cell function will be measured by flow cytometry and innate and adaptive responses measured by whole killed pathogen assay and Toll like receptor ligand assays from whole blood collected at birth (cord), Visit 3 and Visit 9.

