6.9 Visit 7 (Week 14 ±7 days)

The following will be performed/recorded at the trial site, no sooner than 21 days after the previous dose of IP (Visit 5):

- Review AEs.
- Review concomitant medication.
- Review feeding status.

- Review Diarrhoea Log and study reminder card.
- Collect a pre dose blood sample
- Collect a saliva sample
- Vital signs (see section 8.3) within the 60 minutes pre dose.
- Administer 2mL of Mylanta Original® antacid formulation within the 10 minutes pre dose.
- Administer the IP dose.

The following procedures will be performed post dose;

- Administer IPV and any scheduled EPI vaccines other than OPV and rotavirus vaccines according to local guidelines (see section 9.2).
- Vital signs (see section 8.3) will be measured at 15 minutes and 30 minutes post dose (±5 minutes).
- Record any AE.
- Issue kits and containers for stool and diarrhoea samples, and instructions for collection and storage of samples (see section 8.4).

Study staff will contact the parents/guardians (clinic or home visit) the day following dosing, and once on day 3, 4 or 5 following dosing, to review AEs and medications, and collect stool and diarrhoea samples.

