6.11 Visit 9 (Week 18 ±7 days)

The following will be performed/recorded at the trial site, no sooner than 21 days after the previous dose of IP (Visit 7):

- Review AEs.
- Review concomitant medication.
- Review feeding status.
- Review Diarrhoea Log.
- Collect a pre dose blood sample.
- Vital signs (see section 8.3) within the 60 minutes pre dose.
- Administer Rotarix®.
- Administer any scheduled EPI vaccines according to local guidelines (see section 9.2).

Study staff will contact the parents/guardians (clinic or home visit) the day following dosing.

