7 TRIAL ENDPOINTS

Immunogenicity will be assessed through:

- Serum anti-rotavirus IgA response (defined as a ≥3 fold increase from baseline) at each serum collection time-point to 4 weeks after 3 doses of RV3-BB.
- Serum anti-rotavirus IgA levels at each serum collection time point.
- Vaccine take defined as at least a threefold increase in serum anti-rotavirus immunoglobulin A (IgA) from baseline to post IP dosing, or detectable RV3 shedding in stools (by ELISA or PCR) any day from day three to day five following administration of IP.
- Cumulative vaccine take defined as vaccine take observed at the current assessment time point or following any previous dose.
- Anti-rotavirus IgA response (defined as at least a threefold increase from baseline to post IP dosing) at each serum collection time point.
- Anti-rotavirus IgA titres defined as geometric mean titres at each serum collection time point.
- Presence of RV3 shedding in stools (by ELISA or PCR) from day 3 to day 5 following each dose of IP.

Safety and tolerability will be assessed through:

- Adverse Events (AE) in the 28 days following each dose of IP.
- Serious Adverse Events (SAE) during the study.
- Review of episodes of blood in stool.

The exploratory objectives will be assessed through:

- HBGA Lewis and secretor status will be determined by ELISA/PCR on Saliva collected at Visits 1, 3, 5 and 7 and whole blood collected at Visit 9 for non secretor participants.
- Maternal serum IgA and IgG responses will be determined by ELISA on Maternal Serum sample collected pre study or at Visit 1.
- Bacterial taxonomic and genetic functional profiling of stool microbiome will be conducted by 16s rRNA or shotgun sequencing on maternal stool and stool samples collected post administration of IP and at birth (prior to first IP dose).
- B and T cell function will be measured by Flow cytometry and innate and adaptive responses measured by whole killed pathogen assay and Toll like receptor ligand assays from whole blood collected at birth (cord), Visit 3 and Visit 9.

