3.1.2 Safety and tolerability endpoints

Safety and tolerability will be assessed through:

- Unsolicited Adverse Events (AE) in the days 0-28 following each dose of IP.
- Serious Adverse Events (SAE) from the first dose of IP until 28 days post last dose of IP.
- Review of episodes of blood in stool.

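### AE capture can stop up to 7 days before the 28-day window after dose 4 closes, and in the SAP's schedule comparison only the infant arm can lose that time

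*Protocol*

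**What the plan says.** **When capture ends.** Protocol 11.3: "AEs will be captured from the time of first dose of IP until the final study visit". The final visit is Visit 9, at week 18 ±7 days. Protocol 6.11 requires only that it be "no sooner than 21 days after the previous dose of IP (Visit 7"), and Table 1 gives the same floor. Visit 7, where dose 4 is given, is at week 14 ±7 days (Protocol 6.9).

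**What the endpoints need.**
- AEs: Protocol 7 has "Adverse Events (AE) in the 28 days following each dose of IP"; SAP 3.1.2 has "Unsolicited Adverse Events (AE) in the days 0-28 following each dose of IP", as does the synopsis. SAP 16.1.2 summarises AEs starting up to 28 days after each dose.
- SAEs: the synopsis has "Serious Adverse Events (SAE) from the first dose of IP until 28 days post last dose of IP", and SAP 3.1.2 agrees. Protocol 7 says only "Serious Adverse Events (SAE) during the study".
- Diarrhoea: the synopsis and SAP 3.1.1 count episodes to 28 days after the last dose of IP.

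**What happens around and after Visit 9.** Rotarix is given at Visit 9, followed by one staff contact the next day (Protocol 6.11). After the AE period, SAEs considered related to IP are reported if the investigator learns of them (Protocol 11.3). Withdrawn infants are to be assessed about 28 days after their last dose (Protocol 6.12.1); there is no matching rule for infants who complete.

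**Which doses are compared.** SAP 16.1.2 sets doses 1 to 3 in the neonatal schedule against doses 2 to 4 in the infant schedule. Dose 4 is placebo in the three neonatal arms and the third RV3-BB dose in the infant arm (Protocol 10.5).

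**The concern.** The rule for collecting events and the definition of the endpoint do not match. An infant whose Visit 9 falls on day 21 after dose 4 is fully within protocol, but days 22 to 28 of the endpoint window lie beyond the stated end of capture. The analysis would then count an unobserved day as a day without an event.

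In the SAP 16.1.2 comparison the loss can fall on one side only. The neonatal windows follow doses 1 to 3 and close well before Visit 9. The infant windows include dose 4, which is an active dose and the only one whose window study end can cut. Any under-count is therefore in the infant schedule, and describing safety by schedule is a stated secondary objective.

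Rotarix adds an attribution problem. An event in the remaining days of the dose 4 window, for example one reported at the next-day contact, follows a different live rotavirus vaccine. SAP 16.1.2 has no rule for such events.

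**Working it through.** **Inputs.** Visit 7 at week 14 ±7 days, or days 91 to 105. Visit 9 at week 18 ±7 days, or days 119 to 133, and at least 21 days after Visit 7. Visit 7 at least 21 days after Visit 5 (Protocol 6.9). Endpoint window 28 days.

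**1. Nominal gap from dose 4 to Visit 9.** (18 − 14) × 7 = 28 days, exactly the stated window.

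**2. Permitted gap.** Gap = 28 + (u9 − u7), where u7 and u9 are the offsets of Visits 7 and 9 from their nominal days, each from −7 to +7.
- Smallest without the floor: 119 − 105 = 14 days; the floor raises this to 21.
- Largest: 133 − 91 = 42 days.
- Shortfall against 28 days: 0 to 7 days, or 0 to 6 if the next-day contact is counted as capture.

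**3. Doses 1 to 3.** Dose 3 (Visit 5) to Visit 9 is at least 21 + 21 = 42 days. Its 28-day window closes at least 42 − 28 = 14 days before Visit 9, and earlier doses have more room. Only the dose 4 window is exposed.

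**4. Share of infants affected.** The documents give no distribution of visit timing, so this rests on assumption. Take u7 and u9 as independent and uniform on whole days, keeping pairs that meet the 21-day floor. A difference of −k arises from 15 − k pairs.
- All pairs: 15 × 15 = 225.
- Pairs below the floor (k = 8 to 14): 7 + 6 + 5 + 4 + 3 + 2 + 1 = 28. Pairs kept: 225 − 28 = 197.
- Pairs with a gap of 21 to 27 days (k = 1 to 7): 14 + 13 + 12 + 11 + 10 + 9 + 8 = 77.
- Share: 77/197 = 39%, or about 67 of 172 infants per arm.
- Days lost, summing k × (15 − k): 14 + 26 + 36 + 44 + 50 + 54 + 56 = 280.
- Mean loss: 280/77 = 3.6 days among those affected; 280/197 = 1.4 days over all infants.

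**5. Other timing assumptions.**

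| Assumption | Share with gap under 28 days |
|---|---|
| Visit 7 never late and Visit 9 never early | 0% |
| Visit 9 never early, Visit 7 uniform | 28/120 = 23% |
| Normal offsets, SD 1 to 3 days | 36% to 43% |
| Both uniform | 39% |
| Visit 9 booked from Visit 7 + 28 days, uniform ±7 | 7/15 = 47% |
| Visit 7 never early, Visit 9 uniform | 56/92 = 61% |

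These are scenarios, not bounds.

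**6. Does follow-up to 18 weeks of age (Protocol 5.1) close the gap?** No. Dose 4 may be given at day 105, and 18 weeks is day 126, only 21 days later. If capture ran to the later of Visit 9 and 18 weeks of age, the uniform case would fall to 49/197 = 25% (seven permitted pairs for each u7 from 1 to 7).

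**7. Size in the schedule comparison.** Under the uniform assumption the mean loss is 1.4/28 = 5% of the dose 4 window, or 1.4/84 = 1.7% of the infant arm's three windows (3 × 28 = 84 days). For the neonatal arms, doses 1 to 3, it is zero.

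**The case against.** The case for leaving this alone is that the schedule is sound as designed: the nominal gap is 28 days, gaps up to 42 days are allowed, and at worst the last quarter of one window in four is lost. Safety is descriptive, with no formal testing (SAP 7.1.4). The schedule comparison already sets newborns against infants from week 6, so background AE rates differ by age anyway. The only time-specific vaccine risk the protocol describes, intussusception after licensed vaccines, is placed 1 to 7 days after the first dose (Protocol 3.5.1), far from days 22 to 28 after dose 4. The next-day contact and the reporting of related SAEs narrow the gap, and any days recovered follow Rotarix.

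Most of this stands as a limit on size. It does not remove the mismatch. The next-day contact recovers one day. Later SAE reporting is passive and confined to related events, so it does not ascertain an all-cause endpoint. Follow-up to 18 weeks of age still permits a 7-day shortfall.

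Three stronger readings are tempting and are not supported:
- A reader might infer that the 28-day windows cannot be observed for many infants. The documents say nothing about actual visit timing, and the share could be nil.
- A reader might infer that every SAE definition is breached. Protocol 7 counts SAEs during the study, which agrees with 11.3; the conflict is with the synopsis and SAP 3.1.2.
- A reader might infer a material bias between schedules. The direction is clear, but no effect on any conclusion is shown.

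**Conclusion.** The mismatch is real and confined to the tail of the dose 4 window. Following the plan exactly can cut that window by 0 to 7 days for AEs, and likewise for SAEs and diarrhoea as the synopsis and SAP define them. How many infants are affected depends wholly on assumed visit timing; the 39% figure assumes independent, even spread over both windows.

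In the SAP 16.1.2 schedule comparison only the infant arm can lose time, so its AEs may be slightly under-counted. In by-dose and overall summaries, and in SAEs to 28 days after the last dose, the neonatal arms are exposed as well, after a placebo dose. This should be corrected because the inconsistency is plain and cheap to remove; it does not undermine the safety assessment as a whole.

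**What to change.** Reconcile the synopsis, Protocol 6.11, 7 and 11.3, and SAP 3.1.1, 3.1.2 and 16.1.2:
- **Protocol 11.3:** end AE and SAE capture at the later of Visit 9 or day 28 after the last IP dose, and apply the same end to diarrhoea episodes. Add one telephone contact at day 28 when Visit 9 is earlier. This is a new contact, because the weekly contacts in Table 1 run only throughout the study.
- **Protocol 7:** align the SAE period with the synopsis and SAP.
- **SAP 16.1.2:** flag events that start after Rotarix, show the dose 4 window with and without them, and report observed days per dose window by arm.
- **If capture is not extended:** restate the dose 4 window as ending at Visit 9 or day 28, whichever comes first, and report AEs per observed time.

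The cost is wording in both documents and one short contact for some infants. No dosing or visit date changes. The recovered days follow Rotarix, so they complete the window but support only limited attribution to RV3-BB.
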